# 3.1 M3541

M3541 is a highly potent, and selective adenosine triphosphate-competitive inhibitor of the ATM kinase. As a result of the mechanism of action, M3541 enhances the therapeutic effect of DNA DSB-inducing treatment modalities. In vivo, M3541 has been shown to improve the antitumor

C

Document No. CCI
Object No. CCI

efficacy of RT. In contrast, M3541 alone shows very limited activity in nonclinical pharmacodynamics studies.

Further information about the nonclinical data to date can be found in the Investigator's Brochure (IB).

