# 7.3 Efficacy Assessments

For all subjects, tumor response assessment will be performed by CT scan or MRI (if MRI is used, CT of chest is mandatory) of the chest / abdomen / pelvis (plus other regions as specifically required for specific tumor types) and other established assessments of tumor burden if CT / MRI imaging is insufficient for the individual subject. All the scans performed at Baseline and other imaging performed as clinically required (other supportive imaging) need to be repeated at subsequent visits. In general, lesions detected at Baseline need to be followed using the same imaging methodology and preferably the same imaging equipment at subsequent tumor evaluation visits.

A brain CT / MRI scan (either, with contrast preferred) is required at Screening if not performed within the previous 6 weeks. Thereafter brain CT / MRI scan should be performed, if clinically indicated by development of new specific symptoms. A bone scan should be performed at Screening and beyond as clinically indicated. Skin metastasis can be used as target lesions according to RECIST 1.1 using measurements by caliper, if they fulfill RECIST 1.1 for target lesions as described below. The presence of new cutaneous lesions will be considered diagnostic of progression for RECIST 1.1, even if not imaged. For each subject, the Investigator will ensure appropriate assessment of the irradiated lesion to follow for determining response: CT or MRI images of primary and / or metastatic tumor masses, physical examination findings. All available images collected during the study period will be considered for the follow up of the subject (to determine further additional treatment needs). The measure(s) to be chosen for sequential evaluation during the study have to correspond to the measures used to document the progressive tumor status that qualifies the subject for enrollment. The tumor response assessment will be assessed and listed according to the Schedule of Assessments (see Table 1).

Bone scans are to be performed according to local and institutional standards.

The following endpoints will be derived based on appropriate tumor assessments according to RECIST 1.1 overall and for lesions within an irradiated field, including those after the end of study treatment until first assessment of PD:

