• Progression-free survival: time from start of treatment to first assessment of PD or death, whichever is earlier. Subjects alive without PD will be censored at their last tumor assessment, documenting the overall objective response is either complete response (CR), partial response (PR), or stable disease (SD). This rule will also apply to subjects dying later than 12 or 26 weeks

Document No. CC Object No. CC

after their last tumor assessment (ie, censoring subjects who died after 2 missed tumor assessments)

- Objective Response: As assessed by the Investigator using RECIST 1.1
- SoLD: As assessed by the Investigator, using RECIST 1.1 on the irradiated target lesions
- Location of first relapse.

**Follow-up:** During survival follow-up (up to 1 year), further anticancer treatment as well as all subsequent progressions will also be recorded.

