## 8.3.2 Secondary Endpoints

The secondary endpoints are the:

- Occurrence of TEAEs, Grade  $\geq$  3 AEs, SAEs, and deaths according to NCI-CTCAE V4.03 assessed from the first administration of M3541
- Occurrence of abnormal
  - laboratory tests

Document No. CC

• findings during physical examinations (reported as AEs)

- vital signs
- ECGs (including corrected QTc interval)
- Best overall response (BOR) using RECIST 1.1 as assessed by the Investigator every 6 weeks (starting on PTD 42) for the first 6 months, then every 12 weeks thereafter until evidence of disease progression
- Progression-free survival (PFS) time defined as time from the first dose of M3541 to disease progression (using RECIST 1.1 as assessed by the Investigator), onset of other anticancer therapy, or death from any cause
- PK endpoints include:
  - FD 1: maximum observed plasma concentration (Cmax), Cmax/dose, time to reach maximum observed concentration (tmax), t1/2, area under the concentration-time curve from time zero to the last quantifiable sampling time point (AUC(0-last)), AUC(0-last)/dose, area under the concentration-time curve from time zero to 6 hour postdose (AUC(0-6h)), area under the concentration-time curve from time zero extrapolated to infinity (AUC(0-∞)), AUC(0-∞)/dose, oral clearance (CL/F), and apparent volume of distribution during terminal phase (Vz/F)
  - FDs 2 through 9: Predose plasma concentration (Cmin) and approximate Cmax of M3541
  - FD 9 or 10: Minimum observed plasma concentration (Cmin); average plasma concentration (Cavg); Cmax, Cmax/dose, tmax, t1/2, AUC(0-last), AUC(0-last/dose, oral clearance at steady-state (CLss/F), apparent volume of distribution at steady-state (Vss/F), accumulation ratio for area under the concentration-time curve (Racc[AUC]), accumulation ratio for maximum concentration (Racc[Cmax]).

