14.1 Best Overall Response

Population: SAF Analysis Set

The tumor response assessment will be based on "Assessment of disease based on imaging (according to RECIST 1.1)" eCRF page.

The Best Overall Response (BOR) is defined as the best response across all time points evaluated per RECIST 1.1, assessed locally by the investigator every 6 weeks (starting on PTD 42) for the

first 6 months, then every 12 weeks thereafter until determination of Progressive Disease (PD), using the investigator-reported overall response per time point and excluding assessments after tumor surgery.

The order to obtain the BOR is the following: Complete Response (CR), Partial Response (PR), Stable Disease (SD), Progressive Disease (PD), and Not Evaluable (NE). For example, a subject who has SD at the first assessment, PR at the second assessment, and PD at the last assessment has a BOR of PR.

To be considered the best response, SD must also meet the minimum 6 weeks (-7 days) from first day of treatment. If the minimum time is not met, the subject's best overall response depends on the subsequent assessments. For example, a subject who has SD at the first assessment, PD at the second assessment and does not meet the minimum duration for SD, will have a best overall response of PD. The same subject lost to follow-up after the first SD assessment would be considered NE for BOR.

If a subject has missing baseline tumor assessment and/or no tumor assessment on-treatment, BOR will be NE.

The confirmed BOR (BORc) will be also analyzed. In this case, CR and PR need to be confirmed at a subsequent assessment, at least 4 weeks after initial overall response assessment of CR/PR.

Both confirmed and unconfirmed BOR will be summarized by tabulating the number and percentage of subjects with CR, PR, SD, PD or NE.

The Objective Response Rate (ORR) is defined as the proportion of subjects with BOR of PR or CR, and it will be tabulated for both confirmed and unconfirmed BOR by dose level, with 95% CI, calculated using the Clopper-Pearson method.

A spider graph will display the percentage change from baseline in tumor size, defined as sum of lesion diameters (longest for non-nodal lesions, short axis for nodal lesions) for all target lesions (as reported in the "Sum of diameters (according to RECIST 1.1)" eCRF page), against the treatment day for each subject per dose level. Subjects with no baseline tumor assessment or without any post-baseline tumor assessment will not be included.

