14.2 Progression Free Survival Time

Population: SAF Analysis Set

Progression Free Survival (PFS) time is defined as the time (in months) from first administration of trial treatment until the first date of PD or death due to any cause.

It will be based on "Assessment of disease based on imaging (according to RECIST 1.1)", "Survival follow-up / Progression disease", "Subject Status / Survival Follow-up", "Anti-cancer treatment after discontinuation", "Radiotherapy after discontinuation", "Surgery after discontinuation" and "Death" eCRF pages.

PFS will be censored in the following scenarios:

- Subjects who do not experience an event (PD or death) will be right-censored on the date of the last evaluable (non missing and non "Not Evaluable") tumor assessment.
- If an event (progression or death without previously documented PD) is observed after more than 2 missed study visits (using visit days as planned in the protocol for calculation) from last tumor assessment, the patient will be right-censored at the date of the last evaluable tumor assessment.
- Subjects who start new anti-cancer treatment prior to an event will be censored on the date of the last evaluable tumor assessment before anti-cancer therapy is given.
- Subjects who do not have a baseline tumor assessment or who do not have any post-baseline
 tumor assessments will be censored on the date of first dose unless death occurred on or before
 the time of the second planned tumor assessment in which case the death will be considered an
 event.

PFS = (date of PD or death/censoring - date of the first dose + 1)/30.4375 (months).

The date of PFS event / censoring will be defined in Table 7.

Table 7 Progression-free Survival Event / Censoring

PFS Event Status		Censoring	Date of event / censoring	
Progressed or died	Before any planned tumor assessment or within two subsequent scheduled tumor assessments after last response assessment of CR, PR or SD	Event	Minimum(Date of PD, Date of death)	
	Otherwise	Censored	Date of last tumor assessment with outcome CR, PR or SD or date of first dose, whatever is later	

PFS Event Status	Censoring	Date of event / censoring
Neither progressed nor died	Censored	Date of last tumor assessment with outcome CR, PR or SD or date of first dose, whatever is later

PFS: progression-free survival, CR = Complete Response, PR = Partial Response, SD = Stable Disease, PD = Progressive Disease.

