14.3 Sum of Lesion Diameter for Irradiated Lesions

Population: SAF Analysis Set

The sum of lesion diameters (longest for non-nodal lesions, short axis for nodal lesions) for all irradiated lesions will be calculated on the basis of "Tumor assessment (according to RECIST 1.1) - Target lesions" and "Irradiated lesions location" eCRF pages to investigate response of irradiated lesions.

A waterfall plot with all subjects from all cohorts will be provided. Bar height will represent the best percentage change from baseline in sum of diameters, calculated using irradiated lesions only. The confirmed BOR (based on all lesion, i.e. also taking non-irradiated lesions into account) will also be presented as an annotation on each vertical bar. Subjects with no baseline tumor assessment or without any post-baseline tumor assessment will not be included.

In addition, a spider graph to investigate the evolution in time of each target lesion will display the percentage change from baseline in lesion size against the treatment day. One graph per subject will be produced with one curve per lesion, clearly specifying lesion location and distinguishing irradiated from non-irradiated lesions. Subjects with no baseline tumor assessment or without any post-baseline tumor assessment will not be included.

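### In-field response and in-field PFS are promised in Protocol 7.3 but never defined in Protocol Section 8 or the SAP, and the omission is not declared

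*Protocol*

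**What the plan says.** Protocol 7.3 introduces its list of derived efficacy endpoints by saying they will be obtained "according to RECIST 1.1 overall and for lesions within an irradiated field". The list includes "Progression-free survival: time from start of treatment to first assessment of PD or death, whichever is earlier" and "Objective Response: As assessed by the Investigator using RECIST 1.1", followed by SoLD on irradiated target lesions and location of first relapse.

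The statistics section of the protocol is narrower. Section 8.3.2 names "Best overall response (BOR) using RECIST 1.1 as assessed by the Investigator every 6 weeks", and PFS, with no in-field version of either. Section 8.5.3.1 tabulates the response rate by dose level and lists PFS, again without an in-field version. The in-field size endpoint is the exploratory SoLD in 8.3.3.

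The SAP states in section 4 that it is built on Protocol Section 8. SAP 14.1 derives best overall response "using the investigator-reported overall response per time point", and SAP 14.2 runs PFS "until the first date of PD or death due to any cause". SAP 14.3 adds a waterfall plot of irradiated lesions, with each bar annotated by a confirmed response that is "based on all lesion, i.e. also taking non-irradiated lesions into account". SAP section 7 declares two departures from the protocol: the added pain and interference summaries, and the omission of the intermittent schedules.

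**The concern.** A secondary objective is antitumour activity of M3541 combined with radiotherapy. Protocol 3.1.3 gives a local mechanism: ATM inhibition is expected to work where radiotherapy has caused double-strand breaks. Protocol 3.1 adds that "M3541 alone shows very limited activity in nonclinical pharmacodynamics studies". The in-field versions of response and PFS are the ones that match this mechanism, and they are the ones that drop out between Protocol 7.3 and the SAP.

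What is at stake is how the activity data will be read. A subject whose irradiated lesions respond while disease elsewhere grows can be recorded as a non-responder with early progression, and no table will show otherwise. On the irradiated-lesion waterfall, a bar showing clear shrinkage could carry the label PD.

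**Working it through.** The plan gives no figure to reproduce, so the check is a comparison of the texts plus one identity.

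**1. What is promised and what is delivered**

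| Output | Protocol 7.3 | Protocol 8.3 / 8.5.3.1 | SAP 14 |
|---|---|---|---|
| Objective response, overall | yes | yes | yes (14.1) |
| Objective response, in-field | yes | no | no |
| PFS, overall | yes | yes | yes (14.2) |
| PFS, in-field | yes | no | no |
| SoLD of irradiated lesions | yes | yes | yes (14.3) |
| Location of progression | yes | yes | yes (14.4) |

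The gap therefore opens inside the protocol. The SAP follows Section 8 and inherits it, and SAP section 7 does not record it.

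**2. How lesions outside the field enter the overall result**

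Let s be the irradiated share of the baseline sum of target-lesion diameters, and let x_in and x_out be the percentage changes in the irradiated and non-irradiated target lesions. Then

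overall change = s × x_in + (1 − s) × x_out.

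The weight of the non-irradiated target lesions is 1 − s. The documents give neither s nor the number of lesions per subject, so the range is:
- s = 1: weight 0, and the overall change equals the in-field change;
- s = 0: weight 1, and the overall change says nothing about the field.

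If the other target lesions do not change (x_out = 0), the overall change is s × x_in. In-field shrinkage is diluted in proportion to s.

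A new lesion, or progression elsewhere, acts separately from this sum. It makes the overall result PD whatever the irradiated lesions do.

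**3. When out-of-field progression changes the recorded response**

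SAP 14.1 takes the best response over time points up to PD, and confirmation needs a second assessment at least 4 weeks later. The first two scheduled post-treatment tumour assessments in Protocol Table 1 are PTD 42 and PTD 90.
- Out-of-field PD at PTD 42: no overall response is recorded, even if the field is responding.
- Overall PR at PTD 42, out-of-field PD at PTD 90, no scan between: unconfirmed best response stays PR, but the PR is not confirmed.
- Overall PR confirmed, out-of-field PD later: both versions stay PR.

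Overall PFS ends at the out-of-field PD in all three cases, subject to the usual censoring rules.

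**4. Whether the existing in-field outputs fill the gap**

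- The irradiated-lesion waterfall gives best percentage change in target-lesion diameters. It contains no irradiated non-target status, new in-field lesions, confirmation or timing.
- The per-subject spider graphs in SAP 14.3 separate irradiated from non-irradiated target lesions, but assign no response category.
- The irradiated-lesion location listing in SAP 14.1 identifies the lesions only.
- The SAP 14.4 listing flags in-field lesions, but covers only subjects with overall PD and gives locations rather than times to in-field progression.

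None of these is an in-field response or an in-field time to event.

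**The case against.** The strongest reply has four parts.

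*The 7.3 sentence is ambiguous.* It introduces four items, one of which (SoLD) is in-field by definition, while the PFS item censors by reference to the overall objective response. It might mean overall for some items and in-field for others. This stands as a possible reading. It does not rescue the plan, because nothing says which item takes which version, and the sentence as written applies both to all.

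*Much of the in-field course can already be read subject by subject.* With about 3 subjects per cohort, the plots and listings go a long way. This stands in part. A reader might infer that in-field data appear only as diameter plots, which is not so: SAP 14.1 and 14.4 add listings. What is missing is the formal category and the time.

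*Later distant progression does not erase a response.* This stands. A reader might infer that any out-of-field progression turns a responder into a failure. Under SAP 14.1 that happens only if it prevents or precedes the overall response, or precedes its confirmation.

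*In-field results would not settle the question either.* The trial is uncontrolled, so in-field response cannot separate M3541 from radiotherapy, and cohorts are small. For 0 of 3 responders the 95% Clopper-Pearson upper limit is 1 − 0.025^(1/3) = 1 − 0.292 = 0.708, an interval of 0 to 71%. This stands, but it limits the overall response rate equally, and the SAP reports that with the same interval.

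**Conclusion.** The concern holds as a gap between what is promised and what is analysed. In-field objective response and in-field PFS are stated in Protocol 7.3, absent from Protocol 8.3.2 and 8.5.3.1 and from SAP 14.1–14.2, and not declared in SAP section 7. Overall response and PFS can be determined by lesions outside the field. That matters because the expected effect is local.

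A reader might go further and infer that the overall endpoints are driven by unirradiated disease, or mostly measure it. The documents do not support that. Overall RECIST includes the irradiated lesions, their share is not stated, and Protocol 6.5.2 allows radiotherapy to other lesions beyond PTD 7, so out-of-field does not always mean unirradiated. That allowance can also work the other way: SAP 14.1 excludes only assessments after tumour surgery, so radiotherapy given elsewhere could contribute to an overall response.

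The size is modest. Efficacy is descriptive, PFS is only listed under Protocol 8.5.3.1, and the primary DLT endpoint is unaffected. The change should be made because it is promised, fits the mechanism and is cheap, but the trial does not depend on it.

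**What to change.** 1. **SAP 14.1.** Define an in-field best response: RECIST thresholds applied to the irradiated target-lesion sum, combined with irradiated non-target status and new in-field lesions, using the eCRF pages that SAP 14.3–14.4 already draw on. Tabulate the in-field response rate with Clopper-Pearson interval by dose level and overall.
2. **SAP 14.3.** Annotate the irradiated-lesion waterfall with the in-field response.
3. **SAP 14.2.** Add a descriptive listing of time to first in-field progression or death. Censor at the last evaluable tumour assessment when assessments stop after out-of-field PD or new anticancer therapy, including radiotherapy to other lesions where it affects the field, and flag the reason.
4. **Protocol.** Align 7.3 with Section 8. If the sponsor prefers not to produce the in-field versions, SAP section 7 should say they were dropped and why.

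The cost is a few more derivations. The field status of new lesions comes from free text, as it already does in SAP 14.4, and intervals will be wide in small cohorts. A reader might infer that in-field PFS needs no further data. That is doubtful: footnote a of Protocol Table 1 lets tumour follow-up stop at PD or a new treatment, so in-field status after out-of-field PD may go unobserved and the censoring may be informative. For that reason the time-to-event output should stay a listing. In an uncontrolled trial, all of these results remain descriptive.

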#### 7.4 Assessment of Safety

The safety profile of the IMP will be assessed through the recording, reporting and analysis of baseline medical conditions, AEs, physical examination findings including vital signs and laboratory tests as specified in the Schedule of Assessments (see Table 1). Special attention will be paid, during the exam as well as the interpretation of the laboratory results, to the organs which are positioned in the irradiation field. Worsening of a condition within an irradiated area (eg, skin reactions, bleeding) during the DLT evaluation period should be reported as a TEAE with grade and relatedness to RT and / or M3541. Improvements of disease-related symptoms should also be reported as improvement of the observed concomitant condition within an irradiated area (eg, improved pain, reduced bleeding) should be reported on the appropriate efficacy-related eCRF page.

Comprehensive assessment of any apparent toxicity experienced by each subject will be performed from the time of giving informed consent and throughout the study. The Investigator will report any AEs, whether observed by the Investigator or reported by the subject (see Section 7.4.1.2). The reporting period for AEs is described in Section 7.4.1.3.

#### 7.4.1 Adverse Events

#### 7.4.1.1 Adverse Event Definitions

#### Adverse Event

An AE is any untoward medical occurrence in a subject or clinical investigation subject administered a pharmaceutical product, regardless of causal relationship with this treatment. An AE can therefore be any unfavorable and unintended sign (including an abnormal laboratory finding), symptom, or disease temporally associated with the use of a medicinal product, whether or not considered related to the medicinal product.

For surgical or diagnostic procedures, the condition / illness leading to such a procedure is considered as the AE rather than the procedure itself.

In case of a fatality, the cause of death is considered as an AE, and the death is considered as its outcome.

The Investigator is required to grade the severity or toxicity of each AE.

Investigators will reference the NCI-CTCAE V4.03 (publication date: 14 June 2010) and use the general grading (severity / intensity; hereafter referred to as severity) scale below. If a particular AE's severity is not specifically graded by the guidance document, the Investigator is to use the general NCI-CTCAE definitions of Grade 1 through Grade 5 following his or her best medical judgment.

The 5 general grades are:

Grade 1: Mild
Grade 2: Moderate
Grade 3: Severe
Grade 4: Life-threatening or disabling
Grade 5: Death

According to Sponsor convention, any clinical AE with severity of Grade 4 or 5 must also be reported as an SAE as per Section 7.4.1.4; however, a laboratory abnormality of Grade 4, such as hemoglobin decreased or neutrophil count decreased, is considered serious only if the condition meets 1 of the serious criteria described below.

If death occurs, the primary cause of death or event leading to death should be recorded and reported as an SAE. "Fatal" will be recorded as the outcome of this specific event and death will not be recorded as separate event. Only, if no cause of death can be reported (for example, sudden death, unexplained death), the death per se might then be reported as an SAE.

Investigators must also systematically assess the causal relationship of AEs to IMP / study treatment (including radiation therapy) using the following definitions. Decisive factors for the assessment of causal relationship of an AE to the IMP / study treatment include, but may not be limited to, temporal relationship between the AE and the IMP / study treatment, known side effects of IMP / study treatment, medical history, concomitant medication, course of the underlying disease, study procedures.

- **Unrelated:** Not reasonably related to the IMP/study treatment. The AE could not medically (pharmacologically / clinically) be attributed to the IMP / study treatment under study in this clinical study protocol. A reasonable alternative explanation must be available.
- **Related:** Reasonably related to the IMP / study treatment. The AE could medically (pharmacologically / clinically) be attributed to the IMP / study treatment under study in this clinical study protocol.

